4.1. Overall Design

This is a single-site study in healthy participants who will receive a single dose of SC or IV ramucirumab. The study will be participant- and investigator-blinded, randomized, and placebo-controlled (7 ramucirumab:3 placebo per group/dose level). Placebo will be used as a comparator for both IV and SC to allow interpretation of safety and tolerability data following administration.

There will be sentinel dosing in this protocol; the initial 2 participants will be randomized/dosed (1 ramucirumab:1 placebo), and subsequently (the next day), the remaining participants in the group will be dosed. This will be subject to a satisfactory safety review by the investigator. This will occur on the first dose of SC (Group 1).

In Section 4.2, additional rationale is presented for the selection of healthy participants for this investigation.

Participants will be screened within 28 days prior to Day 1 of dosing for each group. Participants will be admitted to the CRU as part of an inpatient visit on Day -1 and will be sequentially enrolled. In each group, participants will be randomized to receive a single dose of IV or SC ramucirumab or placebo (7 ramucirumab:3 placebo per group).

There will be at least a 2-week safety observation period between the titrating SC injection groups (Groups 1 and 2), and between the SC and IV groups (Groups 2 and 3) while local laboratory data is reviewed by the sponsor and investigator. If the safety review is acceptable, Groups 4 and 5 may be dosed simultaneously to Group 3, as no dose escalation is occurring in those groups. Group 6 may be dosed with an infusion pump once the sponsor has reviewed both the safety and PK data (Groups 1 through 3) if the safety results are acceptable and if there is scientific value for investigating an additional group. The dose for Group 6 will be determined (maximum dose 350 mg). The plan for periodic reviews is presented Section 9.5.

The dose levels are provided below and may be adjusted based on safety reviews for preceding groups.

The participants receiving ramucirumab in each group will be administered the following dose level (up to 3 dose levels predicted to be ultimately used for therapeutic intent [see Section 4.3 for dose rationale]):

- **Group 1 will test a ramucirumab 350-mg SC dose**
 - administered at a concentration of 175 mg/mL as 1×2-mL injection.
- **Group 2 will test a ramucirumab 700-mg SC dose**
 - administered at a concentration of 175 mg/mL as 2×2-mL injections.

- **Group 3 will test a ramucirumab IV dose (maximum of 350 mg)**
 - administered as a 60-minute infusion (maximum 35 mL×10 mg/mL).
 - Analysis of safety and PK data from Groups 1 to 3 will allow initiation of Group 6.
- **Group 4 will test a ramucirumab 350-mg SC dose**
 - administered at a concentration of 87.5 mg/mL as 2×2-mL injections
 - The purpose is to investigate the effect of a different drug product concentration on PK and safety and Group 1 will be the reference comparison group.
- **Group 5 will test a ramucirumab 350-mg SC dose**
 - administered at a concentration of 175 mg/mL as 2×1-mL injections
 - The purpose is to investigate the effect of a different volume administered at the injection site on PK and safety and Group 1 will be the reference comparison group.
- **Optional Group 6 may test SC ramucirumab dose, maximum 350 mg, to further understand SC ramucirumab PK and safety in healthy participants**
 - administered at a concentration of 175 mg/mL administered via an infusion pump according to the pharmacy manual.

The SC injection site will be the abdomen. See Section 6.1 for details.

Following the safety review of Groups 1 and 2, the sponsor and investigator agreed to allow doses to be reduced for remaining groups. This may mean that less groups may need to be studied. The asymptomatic transaminase increases observed during the safety review have also lead to a change in the exclusion criteria to further enhance safety of the participants. In view of these findings, subsequent doses will be capped at 350 mg. Lower doses may also be studied. These decisions will be based on emerging data (see Section 4.3 for further details).

Injection site pain (ISP) and ISRs will be monitored in each group, and a comparison of scorings will be used. The severity of ISP and ISRs reported across all participants will be evaluated. The data from Group 1, in comparison to Groups 4 and 5, will provide insight about the effect of injection volumes and ramucirumab concentration on ISP and ISR.

Participants will be discharged from the CRU on Day 8 after all study assessments have been completed and in agreement with the investigator. Participants may be required to remain in the CRU longer than Day 8, at the investigator's discretion. Participants will be required to return to the CRU for clinical assessments and blood samples on an outpatient basis (according to the protocol Schedule of Activities) until the final follow-up visit approximately 12 weeks following the IV infusion or SC injection. The sample size is provided in Section 9.2.

Participants should follow local guidance and CRU precautions to minimize risk for coronavirus disease 2019 (COVID-19) infection.

4.2. Scientific Rationale for Study Design

The healthy population was selected to participate in this study because it is the most optimal setting to gather intensive PK information over an extended period of time. This PK data are needed to answer the scientific objectives of the study, which are to assess the bioavailability of ramucirumab following SC administration. Furthermore, conducting the study in healthy participants mitigates the potential confounding effects of disease state and concomitant medications in patients on the primary objective (PK and safety) of the study. It is very difficult to achieve the study objective in a cancer patient population. Accurate estimation of AUC is critical for robust estimation of bioavailability. Consequently, ramucirumab PK sampling over at least 12 weeks is needed to achieve that goal because of the long terminal half-life of ramucirumab.

Ramucirumab IV administration is important in this study to accurately estimate the bioavailability, because it is not known whether ramucirumab clearance (hence exposure) is similar in healthy participants and cancer patients.

Ramucirumab has not been studied in healthy human participants. However, the large clinical safety database of IV ramucirumab in cancer patients and the preclinical studies with ramucirumab administered IV and SC support investigating single IV and SC ramucirumab doses in healthy participants (see margin of safety in Section 4.3).

Placebo will be used as a comparator to allow optimal interpretation of safety and tolerability data following ramucirumab administration.

The dose justification is provided in Section 4.3.

The rationale for sample size is provided in Section 9.2.

4.3. Justification for Dose

The overall principle for the choice of SC ramucirumab dose levels to be tested in this single-ascending dose study in healthy participants is:

- To support appropriate dose selection in subsequent studies in cancer patients with multiple repeated SC ramucirumab administration
- To support subsequent safe administration, in cancer patients, of ramucirumab SC dosing regimen leading to
 - Higher C_{trough} (target 50 $\mu\text{g}/\text{mL}$) and lower C_{max} for ramucirumab compared to IV ramucirumab 10 mg/kg Q2W
 - Similar steady-state AUC as achieved following IV ramucirumab 10 mg/kg Q2W.

Simulations of PK profiles following SC dosing were performed, taking into account different constraints (for example, maximum possible drug product concentration and maximum possible injectable volume and dose frequency), and the most conservative (worse-case scenario) assumptions for bioavailability and rate of absorption (0.6 bioavailability with coefficient of variation [CV] 20% and rate of absorption of 0.3/day). Those assumptions are based on literature report about mAb PK following SC administration which indicate that 60% bioavailability is in the lower end of reported bioavailability (Viola et al. 2018). The 20% CV on bioavailability lead

to a bioavailability of 0.6 (0.44-0.79), mean (90% population prediction interval), used in these simulations.

All of the outcomes from those simulations, graphs, and tables are presented in [Appendix 6](#) (Section [10.6](#)).

To prepare for future investigation of the above-mentioned ramucirumab SC dosing regimen in cancer patients, the proposed study (Study JVDT) in healthy participants will investigate single doses of SC ramucirumab 350 and 700 mg (with a maximum of 2 mL per injection site and a maximum of 2 injection sites per dose administration). The starting 350-mg SC ramucirumab dose is half the highest approved therapeutic dose (10 mg/kg Q2W IV). To prepare for the need of a loading dose in cancer patients, a ramucirumab dose of 350 mg administered SC (as a slow SC infusion with a pump) may also be investigated in Study JVDT.

The top planned SC ramucirumab dose in Group 6 was initially planned as a maximum dose level of 1400 mg in a previous protocol version. Since then, Groups 1 and 2 (350 mg and 700 mg SC) have been enrolled and received study treatment, and 2-week postdose safety data from those groups were reviewed. Consequently, after the safety review, the maximum dose is to be capped at 350 mg as this dose was associated with an acceptable safety profile. This edict applies to all subsequent groups.

The emerging data suggests Group 6 may not be needed given the planned collection of information at the 350 mg SC dose (Groups 1, 4, and 5).

In addition to those SC ramucirumab dose levels, a single dose of up to 350-mg ramucirumab administered IV (via 60-minute infusion) is planned to enable determination of the absolute bioavailability following SC administration.

The initial ramucirumab SC doses will be determined from the safety data from previous clinical experience with IV ramucirumab, as it is understood that the IV administration leads to higher plasma levels and it is expected that tolerability will be better with the SC administration.

In summary, ramucirumab dose levels that are proposed for Study JVDT are:

- ramucirumab IV, originally 700 mg dose level and subsequently modified to 350 mg IV following safety review of Groups 1 and 2
- ramucirumab 350 mg SC
- ramucirumab 700 mg SC

The table below presents the margin of safety (based on C_{max} or AUC) relative to the toxicology monkey study. The table uses the originally planned maximum ramucirumab dose IV and SC, in the absence of any ramucirumab data in healthy participants and based on the assumption that ramucirumab IV PK properties are similar in healthy participants and in patients and the assumption for bioavailability following SC as stated above.

Predicted Margin of Safety at Maximum Dose in Study JVDT

Study	Dose (mg/kg) and Route of Administration	C _{max} (µg/mL)	Margin of Safety	AUC ₀₋₁₆₈ (mg.h/mL)	Margin of Safety
SNBL 023.04 (5-week monkey)	40 (IV) ^a NOAEL	1460	-	189	-
JVDT (SAD in healthy participants)	10 (IV) ^b	211	7X	18.6	10X
	20 (SC) ^c	139	11X	15.3	12X

Abbreviations: AUC₀₋₁₆₈ = area under the curve during the dosing interval; C_{max} = maximum observed

concentration; IV = intravenous; PK = pharmacokinetics; popPK = population pharmacokinetics; SAD = single ascending dose; SC = subcutaneous.

a 40 mg/kg was the no-adverse-effect level in this study.

b 700 mg is equivalent to 10 mg/kg in a 70-kg human. Exposure values from RELAY popPK model report the mean, as the toxicology data report the mean, which is consistent with the median values reported in [Appendix 6](#).

c 1400 mg is equivalent to 20 mg/kg in a 70-kg human. The human PK model simulation of SC regimen indicates a mean C_{max} of 139 µg/mL and mean AUC over the first week AUC₀₋₁₆₈ of 15.3 mg.h/mL following a ramucirumab 1400-mg SC administration. [Appendix 6](#) reports median value (very close to these mean values).

A NOAEL of 40 mg/kg was established in a 5-week repeat dose study in monkey. At this dose, C_{max} and AUC values are 11-fold and 12-fold higher than the anticipated systemic exposure following a single SC dose of 1400 mg in Study JVDT. At this dose, C_{max} and AUC values are 7-fold and 10-fold higher than the anticipated systemic exposure following a single IV dose of 700 mg in Study JVDT.

Therefore, nonclinical data provides support for the safety of the IV and SC dose of ramucirumab to be investigated in normal, healthy human participants (Section [10.6](#)).

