4.3 Justification of Dose	
Based on the safety review of Groups 1 and 2:
 
 reduced dose from 700 mg IV to a maximum dose of 350 mg IV for Group 3, reduced maximum dose level from 1400 mg to 350 mg for Group 6, indicated Group 6 may not be needed based on emerging data, capped maximum dose at 350 mg for all subsequent groups because of the acceptable safety profile, and added explanation that margin of safety table was based on originally planned doses. 	To enhance the safety of the participants.
5.2 Exclusion Criteria	
For Exclusion Criterion [14]:
 
 removed 1.5-fold for ULN, and added AST and GGT. 	To enhance the safety of the participants based on safety review of Groups 1 and 2.
5.2 Exclusion Criteria	
For Exclusion Criterion [15]:
 
 removed 1.5-fold for ULN, and removed isolated bilirubin >1 fold ULN is acceptable if bilirubin is fractionated and direct bilirubin <35%. 	To enhance the safety of the participants based on safety review of Groups 1 and 2.
5.2 Exclusion Criteria	
For Exclusion Criterion [16]:
 
 removed with exception of Gilbert's syndrome or asymptomatic gallstones, and specified that Gilbert's syndrome is not acceptable. 	To enhance the safety of the participants based on safety review of Groups 1 and 2.
6.1 Study Intervention(s) Administered	
Based on the safety review of Groups 1 and 2:
 
 reduced dose from 700 mg IV to a maximum of 350 mg IV for Group 3, removed 1400 mg SC dose, and removed reference to approximately 30 minute duration for SC infusion (with pump) and added reference to the pharmacy manual. 	To enhance the safety of the participants.

Section # and Name	Description of Change	Brief Rationale
8.2.3 Electrocardiograms	Removed reference to Section 7 for QTc withdrawal criteria and any additional QTc readings.	To remove a reference that was inadvertently included in the protocol.
9.4.2.2 Pharmacokinetic Statistical Inference	Modified the dose range investigated from 350 mg to 1400 mg to 350 mg to 700 mg based on safety review of Groups 1 and 2.	To reflect dose level changes based on safety review of Groups 1 and 2.
9.5 Interim Analyses	Indicated that PK data may be reviewed for Groups 1 and 2 if timing permits.	To add flexibility for reviewing PK data if needed.

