5.2. Exclusion Criteria

Participants are excluded from the study if any of the following criteria apply:

Medical Conditions

1. Have known allergies to ramucirumab, any components of the formulation buffer matrix or related compounds, or history of significant atopy

2. Have an abnormal blood pressure (>140/90 mmHg) and/or pulse rate as determined by the investigator
3. Have a history or presence of cardiovascular, respiratory, hepatic, renal, GI, endocrine, hematological, psychiatric, or neurological disorders that could significantly alter the absorption, metabolism, or elimination of drugs; or constituting a risk when taking the study intervention; interfere with the evaluation of injection site assessments, or any other medical condition that, in the judgement of the investigator, could interfere with the interpretation of data
4. Regularly use known drugs of abuse and/or show positive findings on urinary drug/alcohol screening
5. Have evidence of human immunodeficiency virus (HIV) infection and/or positive HIV antibodies
6. Show evidence of hepatitis C and/or positive hepatitis C antibody
7. Show evidence of hepatitis B and/or positive hepatitis B surface antigen
8. Have self-perceived dullness or loss of sensation on either side of the body or the abdomen
9. Have donated blood of more than 500 mL within the previous 30 days of study screening
10. Have a history or presence of a bleeding disorder
11. Have had a serious or nonhealing wound, ulcer, or bone fracture within 28 days prior to enrollment
12. Have undergone major surgery within 28 days, or have postoperative bleeding complications or wound complications from a surgical procedure performed in the last 2 months
13. Have a history of GI perforation, peptic ulceration, diverticular disease, and/or fistulae within 6 months prior to enrollment
14. Have alanine transaminase, aspartate aminotransferase, and gamma-glutamyl transferase > upper limit of normal (ULN)
15. Have bilirubin > ULN
16. Have current or chronic history of liver disease or known hepatic or biliary abnormalities (Gilbert's syndrome is not acceptable)

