#### 5. STUDY DESIGN

This is a single-site study in healthy participants who will receive a single dose of SC or IV ramucirumab. The study will be participant- and investigator-blinded, randomized, and placebo-controlled (7 ramucirumab:3 placebo per group/dose level). Placebo will be used as a comparator for both IV and SC to allow interpretation of safety and tolerability data following administration.

There will be sentinel dosing in this protocol, the initial 2 participants will be randomized/dosed (1 ramucirumab:1 placebo), and subsequently (the next day), the remaining participants in the group will be dosed. This will be subject to a satisfactory safety review by the investigator. This will occur on both the first dose of SC (Group 1).

Participants will be screened within 28 days prior to Day 1 of dosing for each group. Participants will be admitted to the clinical research unit (CRU) as part of an inpatient visit on Day -1 and will be sequentially enrolled. In each group, participants will be randomized to receive a single dose of IV or SC ramucirumab or placebo (7 ramucirumab:3 placebo per group).

The participants receiving ramucirumab in each group will be administered the following dose level (3 dose levels predicted to be ultimately used for therapeutic intent):

- Group 1 will test a ramucirumab 350-mg SC dose
  - administered at a concentration of 175 mg/mL as 1×2-mL injection.
- Group 2 will test a ramucirumab 700-mg SC dose
  - administered at a concentration of 175 mg/mL as 2×2-mL injections.
- Group 3 will test a ramucirumab IV dose (maximum of 350 mg)
  - administered as a 60-minute infusion (35 mL×10 mg/mL)
  - Analysis of safety and PK data from Groups 1 to 3 will allow initiation of Group 6.
- Group 4 will test a ramucirumab 350-mg SC dose
  - administered at a concentration of 87.5 mg/mL as 2×2-mL injections
  - The purpose is to investigate the effect of a different drug product concentration on PK and safety and Group 1 will be the reference comparison group.
- Group 5 will test a ramucirumab 350-mg SC dose
  - administered at a concentration of 175 mg/mL as 2×1-mL injections
  - The purpose is to investigate the effect of a different volume administered at the injection site on PK and safety and Group 1 will be the reference comparison group.
- Optional Group 6 may test SC ramucirumab dose, maximum 350 mg
  - administered at a concentration of 175 mg/mL administered via an infusion pump according to the pharmacy manual

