### **9.4.3 Clinical laboratory parameters**

All clinical chemistry and hematology data will be summarized by parameter, treatment, group, and dose level, together with changes from baseline, and listed. Urinalysis data will be listed. Additionally, clinical chemistry, hematology and urinalysis data outside the reference ranges will be listed and flagged on individual participant data listings.

Coagulation and thyroid-stimulating hormone data will be listed.

Samples for serum immunoglobulins, and their derived total, will be summarized and listed by parameter and treatment.

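### Group 1 is the safety reference for Groups 4 and 5, but the liver entry criteria were tightened in between, so those liver comparisons mix product presentation with entry criteria and calendar time

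*Protocol*

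**What the plan says.** Protocol Section 4.3 gives the order of events: "Since then, Groups 1 and 2 (350 mg and 700 mg SC) have been enrolled and received study treatment". Protocol Section 4.1 links the next step to what was seen there: "The asymptomatic transaminase increases observed during the safety review have also lead to a change in the exclusion criteria".

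The Amendment (c) summary of changes is the only record of the limits that Groups 1 and 2 entered under. It is used here as history, not as a contradiction of the current text.

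- Criterion 14: the entry is "removed 1.5-fold for ULN, and added AST and GGT". Section 5.2 now reads "Have alanine transaminase, aspartate aminotransferase, and gamma-glutamyl transferase > upper limit of normal (ULN").
- Criterion 15: the 1.5-fold multiple was dropped, and the amendment "removed isolated bilirubin >1 fold ULN is acceptable if bilirubin is fractionated and direct bilirubin <35" per cent. Any bilirubin above ULN now excludes.
- Criterion 16: the exceptions for Gilbert's syndrome and asymptomatic gallstones were dropped. Section 5.2 now states "Gilbert's syndrome is not acceptable".

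SAP Section 5 says that Group 4 tests a different concentration and Group 5 a different volume per site, in each case "on PK and safety and Group 1 will be the reference comparison group". On presentation, SAP Section 9.4.3 says "All clinical chemistry and hematology data will be summarized by parameter, treatment, group, and dose level, together with changes from baseline", and Section 9.4.1 breaks TEAEs down in the same way. SAP Section 6 has a single SC placebo treatment name. Section 9.4.11 plans no safety inference.

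SAP Section 3 lists Amendment (c) among the documents reviewed, and Section 5 mentions the criteria change. No analysis section takes it up.

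**The concern.** Transaminase increases are the reason the dose was capped and the entry criteria changed. Liver injury is an adverse event of special interest (Protocol Section 8.3.6), and safety is a primary objective. The criteria therefore changed on the variable that will be looked at most closely.

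Groups are enrolled in sequence, and randomisation is only within group. Group 1 v Group 4 and Group 1 v Group 5 are non-randomised comparisons across the change. Quieter liver chemistry in Groups 4 and 5 could reflect the lower concentration or smaller volume, the stricter entry limits, or the later calendar period. With the tables as planned, a reader could credit the presentation for what the entry limits produced.

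**Working it through.** **Inputs.** 10 participants per group, 7 active and 3 placebo; about 60 enrolled and at least 48 evaluable (Protocol Section 9.2). Groups 1 and 2 entered before Amendment (c) (Section 4.3). Groups 4 and 5, and optional Group 6, come after it.

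**Plan's own figures.** 6 × 10 = 60 and 6 × 8 = 48; both reproduce. No power or alpha is stated, so there is none to check.

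**Which comparisons cross the change.** Shares entered before Amendment (c), planned numbers:

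| Comparison | Share before the change | Crosses it? |
|---|---|---|
| Group 1 v Group 4, active | 7/7 v 0/7 | Yes |
| Group 1 v Group 5, active | 7/7 v 0/7 | Yes |
| Group 1 v Group 2, active | 7/7 v 7/7 | No |
| Active v placebo within a group | Same version in both arms | No |
| Groups 1+4+5 v Group 2, active, if pooled | 7/21 v 7/7 | Yes, but this pooling is specified for PK only |
| SC placebo, if one column | 6/12, or 6/15 with Group 6 | Mixed: 50% or 40% |

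**Resolution.** One participant is 1/7 = 14.3 percentage points. The comparison with concurrent placebo is clean but imprecise. With no events, the exact two-sided 95% upper limit is 1 − 0.025^(1/n): 41% for n = 7 and 71% for n = 3.

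**Illustration 1: entry effect alone, no product effect.** The rates are assumptions. Group 1 minus Group 4 (or 5) is the difference in rates; multiplied by 7 it gives expected participants.

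| Earlier v current rate | Spurious difference | Expected participants | Shift in a pooled SC placebo rate (with Group 6) |
|---|---|---|---|
| 10% v 5% | 5 points | 0.35 | 2.5 (2) points |
| 20% v 10% | 10 points | 0.7 | 5 (4) points |
| 30% v 10% | 20 points | 1.4 | 10 (8) points |

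An entry effect of this size is about one participant, which is also the smallest difference the comparison can show.

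**Illustration 2: how many might have entered above ULN.** Assume ALT/ULN among candidates is log-normal with log-SD s, and a fraction p lies above 1, so μ = −s·z(1−p). Of those eligible at a limit of 1.5, the fraction above 1 is f = 1 − Φ(−μ/s) / Φ((ln 1.5 − μ)/s).

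Worked case, p = 0.05 and s = 0.35: μ = −0.576 and f = 1 − 0.950/0.9975 = 0.048. The chance of at least one such participant among the 10 in Group 1 is 1 − (1 − 0.048)^10 = 39%.

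Over p from 0.025 to 0.15 and s from 0.35 to 0.5:

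- f runs from 2% to 14%;
- the chance of at least one in Group 1 runs from 20% to 77%, and in Groups 1 and 2 together (20 people) from 36% to 95%;
- mean baseline ALT is 3% to 14% higher under the 1.5-fold limit.

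None of these inputs is in the documents. The model covers ALT only and ignores inclusion criterion 3, which could lower the figures.

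**The case against.** The strongest case is that the plan already limits the damage.

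- Chemistry and TEAEs are broken down by group, and chemistry is shown as change from baseline.
- Reference-range flags appear only in individual listings, where a raised baseline is visible.
- A TEAE must occur or worsen after dosing (SAP Section 9.4.1), so an unchanged raised baseline does not count.
- Inclusion criterion 3 asks for normal laboratory results or deviations judged not clinically significant, and no amendment log lists a change to it.
- Protocol Section 4.1 describes the Group 1 v Groups 4 and 5 tolerability comparison in terms of injection-site pain and reactions.
- Extra safety analyses are allowed if the data warrant them (Protocol Section 9.4.1.2).

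Most of this stands, and it rules out some stronger readings:

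- A reader might infer that the 350 v 700 mg contrast is confounded. Groups 1 and 2 both entered before the change. Combining Groups 1, 4 and 5 is specified only for PK (Protocol Section 9.4.2.2, SAP Section 9.3.2).
- A reader might infer from the single SC placebo name that placebo will be pooled across the change. The by-group wording points the other way; the layout only needs confirming.
- A reader might infer that fewer out-of-range values in Groups 4 and 5 would be wholly an entry effect. No such count is planned as a summary, and no document figure supports wholly.

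What the objection leaves standing is the Group 1 reference itself. Both documents name safety, not only injection-site tolerability, as its purpose. Tables by group still set Group 1 beside Groups 4 and 5 across the change. Change from baseline does not remove a different susceptibility to later increases, and SAP Section 9.4.3 does not define the laboratory baseline. An analysis left to judgement after review is weaker than one specified now.

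**Conclusion.** The point holds for descriptive liver comparisons of Group 1 with Groups 4 and 5. Presentation and entry-criteria version coincide completely (7 of 7 v 0 of 7 active), and calendar time runs with them. This limits interpretation; it is not an error-rate problem, since no safety test is planned.

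The effect on actual liver status is unknown, because the number in Groups 1 and 2 who would fail the current limits is not given and may be none. The conclusion assumes planned numbers and no Group 1 replacement enrolled after the amendment. It also assumes that criterion 14 is meant to be stricter: as written, *and* joins the three enzymes, which read literally requires all three to be raised. Criteria 15 and 16 are stricter on any reading.

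**What to change.** 1. In SAP Sections 9.4.3 and 9.4.1, add a supportive repeat of the planned ALT, AST, GGT and bilirubin summaries (values and change from baseline) and of hepatic TEAE counts. Restrict it, in every group and both arms, to participants with each of the four tests not above ULN at a named baseline and with no Gilbert's syndrome or other hepatic or biliary history. The last predose value would serve as baseline; by the schedule that is Day −1. Keep the full-set tables beside it.
2. Treat this as the definition of an analysis set only. The conjunction in criterion 14 should be reconciled separately; no eligibility rule is proposed here.
3. Confirm that SC placebo liver and TEAE tables are shown by group, or as Groups 1–2 v Groups 4–6, and not only as one pooled column.
4. State in the CSR that Group 1 v Groups 4 and 5 liver differences are non-randomised and cross a change in entry criteria, and read them with each group's concurrent placebo.

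The cost is a few tables from screening, Day −1 and medical-history data already collected. The restricted set may be smaller than 7 active and 3 placebo per group. It does not remove calendar-time differences, which is why the CSR statement is needed as well. If nobody in Groups 1 and 2 is dropped, the tables will show that and settle the baseline question.
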